**Table 5-3 Factors and Covariate for imputation model**

Factors and covariates at baseline	Type	Categories	Order
Sex	Factors	Female, Male	1
Region	Factors	Asia, Europe, North America, Oceania	2
Tanner stage	Factors	Part A: Stage 2 and 3 together, Stage 4 and 5 together Part B: Stage 1 with or without premature adrenarache	3
Glycaemic category	Factors	Yes, No	4
Glycaemic category, Tanner stage	Interaction factor	Not applicable	5
BMI SDS	Covariate	Not applicable	6

The multiple imputations will be generated using Novo Nordisk trial number 80224179 as seed number.

If the imputation ANCOVA model cannot be estimated due to too few placebo subjects with available data, explanatory variables will be removed in the following order until the model is estimable: region, sex, baseline BMI SDS, Tanner stage, baseline glycaemic category and interaction between baseline glycaemic category and stratification factor for Tanner stage.

**Table 5-4 Statistical analysis to address primary objectives**

SI No.	Endpoints	Landmark visits	Endpoint type	Imputation approach and Statistical model	Analysis set	Sensitivity analyses
Primary Endpoint						
1	Change from baseline in BMI SDS	Week 16, Week 52	Continuous	J2R-MI ANCOVA	FAS	
 
• ANCOVA (LOCF)
 
• ANCOVA (BOCF)
 
• ANCOVA (no imputation, with 16-week (or 52 weeks) completers)
 
• MMRM
 

Due to the outbreak of the coronavirus (COVID-19), the primary endpoint assessments (body weight and height) for very few subjects could not be performed on-site at the end of the double-blind period of the trial – Visit 10 (Week 16) or at the end of the open-label period of the trial – Visit 19 (Week 52). It was recommended to have the body weight and height measured at the subject's family doctor, if possible, and alternatively to perform home weight and height measurements based on instructions provided. These measurements as well as measurements for subjects who were unable to perform or have body weight and height measured due to COVID-19 will not be part of the primary analysis but will be included in sub analysis. This is applicable only for part B as only subjects from part B were enrolled in the trial during the pandemic.

### 5.3.3 Sensitivity analysis

To investigate the sensitivity of the results of the main analysis of the primary endpoint about the handling of missing data, the following sensitivity analyses will be performed.

An ANCOVA will be performed with imputation of missing values according to the last observation carried forward (LOCF) method. The model will include factors, covariates and interaction term as listed in [Table 5-1](#). The response variable will be the last available measurement of BMI SDS obtained within the 16-week double-blind period of the trial. Data from nominal visits (V10x and V19x) will not be used for this analysis.

Statistical Analysis Plan  
Trial ID: NN8022-4179  
UTN: U1111-1162-7884  
EudraCT No: 2014-004415-37

~~CONFIDENTIAL~~

Date:	14 December 2020	Novo Nordisk
Version:	1.0	
Status:	Final	
Page:	17 of 36	

- The same type of ANCOVA as above will be performed but using an imputation of missing values according to the baseline observation carried forward (BOCF) method. Missing measurements of BMI SDS at 16 weeks will with this method be imputed by the corresponding baseline values. Data from nominal visits (V10x and V19x) will not be used for this analysis.
- The same type of ANCOVA as above will be performed without imputation by only including subjects who completed the 16-week double-blind period. Data from nominal visits (V10x and V19x) will not be used for this analysis.
- A mixed model for repeated measurements (MMRM) will be applied where all post baseline BMI SDS measurements obtained at planned visits during the 16-week double-blind period will enter as the dependent variables, and the factors, covariates and interaction term as listed in [Table 5-1](#) will be included in the model. . All these factors and covariates will be nested under visit, which is technically the same as introducing the corresponding interaction terms in the model. An unstructured covariance matrix for the BMI SDS measurements within subject will be employed. Data from nominal visits (V10x and V19x) will not be used for this analysis.

The sensitivity analyses will be repeated for the week 52 co-primary endpoint.

The ANCOVA model with LOCF assumes that post treatment discontinuation, the body weight is on average stable in both treatment arms. If the assumption holds, the treatment effect (effectiveness estimand) in each arm and the treatment difference can be estimated from this analysis unbiased. If the withdrawal and the development in both arms are similar, the treatment difference can be estimated from this analysis unbiased. If the development in body weight after treatment discontinuation differs between active and placebo, this analysis might provide an optimistic or over-conservative estimate, depending on the actual circumstances. The analysis is included to be able to compare the results with legacy obesity programs, where this analysis was the main analysis of the primary endpoints.

The ANCOVA model with BOCF assumes that post treatment withdrawn subjects with missing values returns to a body weight in the proximity of their baseline body weight regardless of the timing of withdrawal. This analysis is expected to provide a conservative estimate (effectiveness estimand) of the treatment effect (in each arm). The impact of this assumption on the treatment difference depends on withdrawal pattern over time and development of body weight post withdrawal and reason for withdrawal. The analysis is typically expected to provide a conservative estimate of the treatment difference (effectiveness estimand).

The ANCOVA analysis in completers is expected to give more positive results than the primary analysis. However, this analysis has its own clinical interpretation and will serve as a benchmark and provide an estimate of the efficacy estimand in the population that tolerate the trial product and endure the diet and exercise counselling program.

The MMRM model assumes that withdrawn subjects, had they completed the trial, would not have behaved differently than completing subjects from the same treatment arm with the same baseline characteristics and change in body weight at time of withdrawal. This analysis estimates the treatment difference had all subjects stayed on the randomised treatment (efficacy estimand).

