**Novo Nordisk**

Body weight measured at V2 is used for the calculation of BMI to evaluate inclusion criteria. Body weight measured at V3 is used as baseline for assessment of change in body weight.

BMI is calculated in the eCRF.

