#### 1.1.2.2 Secondary endpoints

##### 1.1.2.2.1 Key supportive secondary efficacy endpoints

- Percent of subjects achieving  $\geq 5\%$  reduction in baseline BMI at weeks 16 and 52
- Percent of subjects achieving  $\geq 10\%$  reduction in baseline BMI at weeks 16 and 52

Change from baseline to 16 and 52 weeks in:

- BMI
- Body weight (kilogram (kg), pounds (lb) and percent (%))
- Hyperphagia score:
  - total score and
  - hyperphagic behaviour, drive and severity score
- Systolic and diastolic blood pressure
- Glucose metabolism: glycosylated haemoglobin (HbA1c), fasting plasma glucose (FPG)

Further details are described in the protocol section 4.2.

Specifications of tables, figures and listings (TFL) and other specifications not included in this SAP will be described in the statistical programming specification (SPS).

Statistical Analysis Plan  
Trial ID: NN8022-4179  
UTN: U1111-1162-7884  
EudraCT No: 2014-004415-37~~CONFIDENTIAL~~Date: 14 December 2020  
Version: 1.0  
Status: Final  
Page: 7 of 36  
Novo Nordisk

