## 6.3 Appendix 3: Definition and calculation of endpoints, assessments and derivations

### 6.3.1 Endpoint derivations and assessments

#### 6.3.1.1 BMI Standard deviation score (BMI SDS) and Height Standard deviation score (Height SDS)

BMI SDS and height SDS score will be calculated using external reference data on BMI and height from WHO

The following procedure is recommended to calculate a z-score for an individual child with measurement  $y$  at age  $t$ :

1: Calculate

$$Z_{\text{ind}} = \frac{[y/M(t)]L(t) - 1}{S(t) L(t)}$$

2: Compute the final z-score ( $Z_{ind}^*$ ) of the child for the indicator as:

$$z_{ind}^* = \begin{cases} z_{ind} & \text{if } |z_{ind}| \leq 3 \\ 3 + \left( \frac{y - SD3pos}{SD23pos} \right) & \text{if } z_{ind} > 3 \\ -3 + \left( \frac{y - SD3neg}{SD23neg} \right) & \text{if } z_{ind} < -3 \end{cases}$$

Where:

- L(t), M(t) and S(t): Box-cox power, median and CV respectively
- y: Individual BMI or height value
- SD3pos: is the cut-off 3 SD calculated at t (age) by LMS method:  
 $SD3pos = M(t)[1 + L(t) * S(t) * (3)]^{1/L(t)}$
- SD3neg: is the cut-off -3 SD calculated at t by the LMS method:  
 $SD3neg = M(t)[1 + L(t) * S(t) * (-3)]^{1/L(t)}$
- SD23pos: is the difference between the cut-offs 3 SD and 2 SD calculated at t by LMS method:  
 $SD23pos = M(t)[1 + L(t) * S(t) * (3)]^{1/L(t)} - M(t)[1 + L(t) * S(t) * (2)]^{1/L(t)}$
- SD23neg: is the difference between the cut-offs -2 SD and -3 SD calculated at t by LMS method:  
 $SD23neg = M(t)[1 + L(t) * S(t) * (-2)]^{1/L(t)} - M(t)[1 + L(t) * S(t) * (-3)]^{1/L(t)}$

To illustrate the procedure, an example with BMI-for-age for boys is provided below and displayed in [Figure 6-1](#).

[figure not shown]

Figure 6-1 Examples of children/adolescents ranked according to the 2007 WHO BMI-for-age reference.

Statistical Analysis Plan  
 Trial ID: NN8022-4179  
 UTN: U1111-1162-7884  
 EudraCT No: 2014-004415-37

~~CONFIDENTIAL~~

Date: 14 December 2020  
 Version: 1.0  
 Status: Final  
 Page: 31 of 36

Novo Nordisk

Child 1: 11-year-old boy with BMI=30

$L=1.7862$   $M=16.9392$   $S=0.11070$

$$Z = \frac{[30.0/16.9392]^{(-1.7862)} - 1}{0.11070 * (-1.7862)} = 3.24 > 3$$

$$SD3 = 16.9392 * [1 + (-1.7862) * 0.11070 * (3)]^{1/(-1.7862)} = 28.03$$

$$SD2 = 16.9392 * [1 + (-1.7862) * 0.11070 * (2)]^{1/(-1.7862)} = 22.45$$

$$SD23 = 28.03 - 22.45 = 5.58$$

$$Z_{ind}^* = 3 + (30 - 28.03/5.58) = 3.35 \text{ (BMI SDS)}$$

Similar calculation will be done for height SDS.

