### 6.3.2.3 For parameters which are not collected at every visit (e.g. HEIGHT):

Visit windows defined in [Table 6-2](#) will be combined. For example [Table 6-3](#) show visit windows for HEIGHT.

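### Does the unstated height for BMI SDS at weight-only visits empty the week-16 MMRM of content?

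*SAP*

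**What the plan says.** **Model.** SAP 5.3.3 describes an MMRM in which "all post baseline BMI SDS measurements obtained at planned visits during the 16-week double-blind period will enter as the dependent variables". All Table 5-1 terms are nested under visit and the covariance is unstructured. The stated assumption is that withdrawn subjects would have behaved like completers "from the same treatment arm with the same baseline characteristics and change in body weight at time of withdrawal". The section adds: "The sensitivity analyses will be repeated for the week 52 co-primary endpoint".

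**Schedule.** The protocol flow chart (section 2) has body weight at every visit from V2 onward. Height is taken at V2 and V3 and next at V10. SAP 6.3.2.3 treats height as a parameter not collected at every visit. After V10, Table 6-3 lists it at V13, V16 and V19. The flow chart as extracted appears to mark V12 in place of V13; the count is the same.

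**Derivation.** SAP 6.3.1.1 gives the LMS z-score with "y: Individual BMI or height value" and no source for the height behind an interim BMI. Protocol 8.4.1.1 says only that "BMI is calculated in the eCRF". SAP 1.1.2.2.1 states that "other specifications not included in this SAP will be described in the statistical programming specification (SPS".

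**The concern.** The MMRM is the one planned week-16 sensitivity analysis meant to use the course before withdrawal to estimate the effect had everyone stayed on treatment. If BMI SDS exists only where weight and height were both scheduled, V10 is the only post-baseline value by week 16. The MMRM then has nothing to condition on and repeats the completer ANCOVA. A reader who saw the two agree would take an identity for robustness. LOCF would suffer too: most early dropouts would have only baseline to carry forward, so LOCF would approach BOCF. Week 16 is the first endpoint in the hierarchy and the only placebo-controlled comparison, so four checks shrinking towards two would be a real loss if it happened.

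**Working it through.** **1. The plan's own figure.** Inputs from protocol 17.1: difference 0.23, SD 0.25, withdrawal 10%, allocation 2:1, power 80%, two-sided 5%.
- Corrected difference: 0.9 × 0.23 = 0.207.
- Corrected SD: √(0.25² + ⅔ × 0.1 × 0.9 × 0.23²) = 0.2563.
- A two-sample t-test with 38 v 19 has power 80.6%, and 57 is the smallest total at 2:1 that reaches 80%. All 27 cells of Table 17-1 reproduce.

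No interim height enters. Nor does one enter the primary analysis: the imputation model in SAP 5.3.2.2 uses baseline terms and the week-16 or week-52 value, all from visits with a scheduled height.

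**2. Visits at issue.** Scheduled heights alone give BMI SDS at 1 of 7 double-blind visits (V4–V10) and at 4 of 16 post-baseline visits to week 52 (V4–V19). At 10% withdrawal, about 6 of 57 subjects (4 liraglutide, 2 placebo) would add nothing to a V10-only model.

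**3. The identity.** With one visit the unstructured matrix is a single variance and REML is ordinary least squares. I simulated 57 subjects (38:19), 6 lost by week 16 and the 13-parameter Table 5-1 model. The first run gave:

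| Analysis | Estimate | SE |
|---|---|---|
| Completer ANCOVA | −0.31353 | 0.08257 |
| MMRM, V10 only | −0.31353 | 0.08257 |
| MMRM, V10 plus early end-of-treatment records | −0.31353 | 0.08257 |
| MMRM, interim values filled | −0.30924 | 0.08040 |

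Over six runs the first three rows always agreed, and the filled model differed from them by 0.001 to 0.028. The identity needs the same subjects in both analyses. SAP 6.3.2.4 sends withdrawn subjects' records to normal visits, so a record in the V10 height window (day 107 to 190) could enter the MMRM but not the completer set. That should be rare.

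**4. What the one-visit reading could cost.** Assumed, not in the documents: correlation ρ of 0.6 to 0.9 between weeks 8 and 16. SE = 0.25 × √(1/34 + 1/17) = 0.074.
- Dropout unrelated to earlier change, or alike in both arms: no shift.
- Half the liraglutide dropouts are the worst at week 8: ρ × 0.25 × φ(1.645)/0.95 = 0.016 to 0.024.
- All of them are: ρ × 0.25 × φ(1.2816)/0.90 = 0.029 to 0.044, at most 0.6 SE and 19% of 0.23.

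**5. What the choice of height rule could cost.** Assumed: height 140 cm and growth 5 cm/year. BMI 30 and SD23 = 5.58 come from the worked example in SAP 6.3.1.1.
- Growth by week 12: 5 × 84/365 = 1.15 cm.
- BMI overstated by (141.15/140)² − 1 = 1.65%.
- In BMI SDS: 30 × 0.0165/5.58 = 0.089 (0.035 to 0.124 for 2 to 7 cm/year).

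This is the week-12 gap between carrying the V3 height forward and using a height that follows linear growth. An equal shift in both arms goes into the visit terms of the MMRM. In LOCF it stays with dropouts only: for a 10-point difference in dropout, at most 0.10 × 0.124 = 0.012, or 5% of 0.23.

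**6. Which reading the text supports.** A one-visit model has no visit for terms to be nested under, no within-subject matrix to leave unstructured, and no change at withdrawal to condition on. SAP 5.3.3 specifies all three, and weight is on file at every planned visit. Only the reading with interim values makes sense of the section.

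**The case for a change.** The case for amending the SAP is that a rule deciding whether a named analysis has one time point or seven belongs in the plan, and that one sentence would settle it. SAP 5.3.2.2 names weight and height together as the primary endpoint assessments, so a programmer could take BMI SDS to exist only where both were measured. The height window of day −2 to 106 for V3 in Table 6-3 does not fill the gap: it allocates height records, and SAP 6.3.2.2 limits windowing to V10 and V19 records of discontinued or withdrawn subjects.

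The omission stands. The inference that the choice remains open until the data are seen does not: BMI is computed in the eCRF and further specifications go to the SPS, and neither is available to read.

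On LOCF, most of the apparent gap is already closed. SAP 6.3.2.4 moves discontinuers' reallocated BMI SDS to the x visits, which SAP 5.3.3 excludes. Under Table 6-3 a record before day 107 maps to V3, where SAP 6.3.3 prefers the collected V3 record. What is left is whether Table 6-2 or Table 6-3 governs BMI SDS.

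One practical limit also stands. SAP 5.1 repeats every analysis by part. With all 16 visits filled, Part B needs 9 + 15 = 24 coefficients at the last visit (9 terms if all four regions occur) against 19 expected completers in Table 17-2, so that unstructured model could not be fitted. The four scheduled-height visits would need 9 + 3 = 12. For all subjects the full model needs 13 + 15 = 28 against 47 expected. This concerns a by-part repeat of a week-52 sensitivity analysis, where a failure to fit would be evident and would have to be reported.

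**Conclusion.** This is missing detail that an analyst following SAP 5.3.3 would fill sensibly, so no change is called for. Interim BMI SDS would be formed from each visit's weight with the last measured or an interpolated height, by one rule for both arms. Choosing between those two is a matter of preference: on assumed growth of 2 to 7 cm/year they differ by 0.035 to 0.124 BMI SDS at week 12, largely absorbed by visit terms in the MMRM and worth at most about 0.012 on the LOCF difference.

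The collapse of the week-16 MMRM into the completer analysis is exact if V10 is the only post-baseline value and both use the same subjects, but it follows from a reading that the section contradicts. Even then the effect lies between 0 and 0.044 BMI SDS, and the non-zero values need an assumed correlation and dropout selective in one arm, which no passage suggests. The week-52 MMRM would not collapse, since four post-baseline heights are scheduled. Only sensitivity analyses are touched; the primary jump-to-reference analysis, the hierarchical test and the sample size are not.

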## 5.4 Secondary endpoints analysis

All the secondary supportive efficacy endpoints listed below will be analysed as per protocol section 17.4.

### 5.4.1 Supportive secondary endpoints

#### 5.4.1.1 Efficacy endpoints

##### BMI

The changes in BMI from baseline at 16 and 52 weeks will be analysed separately with the same type of ANCOVA with MI as used for the main analysis of the primary endpoint, but with the baseline BMI as covariate instead of the baseline BMI SDS.

In addition, the following categorical endpoints related to BMI will be evaluated:

- Percentage of subjects achieving  $\geq 5\%$  reduction in baseline BMI at 16 weeks
- Percentage of subjects achieving  $\geq 5\%$  reduction in baseline BMI at 52 weeks
- Percentage of subjects achieving  $\geq 10\%$  reduction in baseline BMI at 16 weeks
- Percentage of subjects achieving  $\geq 10\%$  reduction in baseline BMI at 52 weeks

These endpoints will be analysed separately using a logistic regression model. The response will be a binary outcome (yes/no) indicating for each subject whether the respective minimum reduction in BMI has been achieved. The model will include treatment, baseline glycaemic category, stratification factor for Tanner stage and baseline BMI and baseline age as covariates. The treatment differences will be presented as odds ratios together with the associated 95% CIs.

For the analysis of the categorical endpoints, missing BMI values will be imputed using the 1000 complete datasets from the MI performed for the corresponding analysis on the continuous change in BMI. The logistic regression will be performed on each of these datasets. Rubin's formula will then be applied on the 1000 estimates of the log odds ratio and the associated SDs to produce a pooled estimate and SD. These pooled values will lastly be used to calculate the 95% CI for the odds ratio.

During the blinded review of data it has been observed that there were only few subjects achieving  $\geq 10\%$  reduction in baseline BMI at week 16 or at week 52.

- Part A: No subject at week 16 and 2 subjects at week 52 experienced a  $\geq 10\%$  reduction in baseline BMI .
- Part B: 2 subjects at week 16 and 3 subjects at week 52 experienced a  $\geq 10\%$  reduction in baseline BMI .

Because of these findings the statistical analysis (J2R-MI Logistic Regression) will not be performed for this endpoint and will only be summarised descriptively.

### **BMI SDS: No increase**

The percentage of subjects with no increase in BMI SDS at 16 and 52 weeks will be analysed using the same statistical method as the one used for the categorical endpoints related to BMI, but with the baseline BMI SDS as covariate instead of the baseline BMI.

### **Hyperphagia questionnaire outcome**

The questionnaire on hyperphagia will be evaluated similarly to the primary endpoint. That is, the change in hyperphagia score (hyperphagia total score and hyperphagic behaviour, drive and severity score respectively), from baseline at 16 and 52 weeks will be analysed separately using the same type of ANCOVA with MI as used for the main analysis of the primary endpoint, but with the corresponding baseline hyperphagia score instead of the baseline BMI SDS as covariate.

### **Glycaemic category**

The change in glycaemic category (normoglycaemia, pre-diabetes, T2DM) from baseline at 16 and 52 weeks will be summarised using descriptive statistics.

Furthermore, two separate analyses will be performed on the binary variable normoglycaemia (yes/no) at 16 and 52 weeks, using a logistic regression model with the factors treatment, baseline glycaemic category, stratification factor for Tanner stage and baseline age as covariate. Missing data will be handled by a MI method like the one used for the main analysis of the primary endpoint but adapted to the logistic regression model. The treatment differences will be presented as odds ratios together with the associated 95% CIs.

### **Other efficacy endpoints**

The following other efficacy variables will be evaluated:

- Body weight
- Waist circumference
- Waist to hip circumference ratio
- CV biomarker (hsCRP)
- Fasting lipids (TC, LDL-cholesterol, HDL-cholesterol, non-HDL cholesterol, VLDL cholesterol, TG and FFA)
- Systolic and diastolic blood pressure
- Quantitative glucose metabolism parameters (HbA1c, FPG, fasting insulin, C-peptide, HOMA-B and HOMA-IR)

The changes in these variables from baseline at 16 and 52 weeks will be analysed using the same type of ANCOVA with MI as used for the main analysis of the primary endpoint, but with the baseline value of the corresponding variable instead of the baseline BMI SDS as covariate. Each endpoint will be analysed separately. For hsCRP, fasting lipids, fasting insulin, C-peptide, HOMA B and HOMA IR, the response and baseline values will be log transformed prior to the analysis.

Categorical responses will be a binary outcome indicating for each subject whether the respective endpoint is achieved. Missing data will be handled by a MI method similar to the one used for the main analysis of the primary endpoint, but adapted to the logistic regression model. The treatment differences will be presented as odds ratios together with the associated 95% CIs.

For missing glycaemic category, the imputation will be done for missing FPG and HbA1c assessments using the imputation model mentioned in [Table 5-5](#).

In addition to all the supportive secondary efficacy analysis following added endpoints will be analysed similarly as per primary endpoint statistical model mentioned in protocol section 17.3.

- Change from baseline at 16 and 52 weeks:
  - BMI SDS (%)
  - BMI (%)

